10.2. Notification

The investigator or designee **must notify all AAGs, regardless of whether or not they are considered drug-related or planned**, to the head of the CTU. [name] ([contact]) [contact] [name] [REDACTED] in order to notify local and national health authorities **within one working day of becoming aware of the event**, so that the contact of the designated promoter can prepare the corresponding written report. AAGs occurring will be reported at any time from the subject's inclusion in the study and up to 30 days after the study has been completed or discontinued. In the specific case of selection failure, the AAGs will be recorded from the moment the consent is signed until the subject is considered a selection failure.

Regardless of the classification of adverse effects, the Investigator must collect all the AEs in the corresponding section of the study data collection notebook (CRD) and fill in all the information pertaining to them.

The sponsor must notify in an EXPEDITIOUS manner all relevant SAFETY INFORMATION, i.e. that could modify the risk/benefit ratio of the investigational medicine, or determine changes in its administration schedule or in the conduct of the trial, for example:

- a qualitative change or an increase in the percentage of occurrence of expected RAGs, which is considered clinically important.
- RAGIs that occur after the completion of a clinical trial and that are notified by the investigator to the sponsor.
- New developments related to the conduct of the trial or the development of the investigational medicinal product and likely to affect the safety of the subjects, such as:
 - Serious adverse events that may be associated with the trial procedures and may modify the conduct of the trial
 - A significant risk to subjects such as the lack of efficacy of an investigational drug used for the treatment of a life-threatening disease.
 - Important new safety findings from new animal studies (such as cardiogenicity).
 - Any premature termination or temporary halt of a clinical trial with the same investigational medicinal product for safety reasons, carried out in another country and by the same sponsor.
 - GRAs related only to an MNI that are considered relevant as they are not subject to RAGI's general rules of expedited reporting of individual cases.
- Any recommendations from the data monitoring committee, which are relevant to the safety of the subjects.

This information must be notified as soon as possible and no later than 15 days after the promoter has become aware of it. In addition, if additional information that is relevant is obtained, it must be notified as quickly as possible.

10.3 Evaluation of toxicity parameters

The classification system for drug toxicity is set out in the DAIDS Table for Grading the Intensity of Adverse Events in Adults and Children, which can be found on the DAIDS RSC website: <http://rsc.tech-res.com/safetyandpharmacovigilance/>.

Treatment of ATRIPLA side effects

The dose reduction levels of ATRIPLA® are indicated in the summary of product characteristics. (see annexes to the protocol)

10.4 COMMUNICATION TO RESEARCHERS

The sponsor shall communicate to investigators any information that may affect the safety of the trial subjects as soon as possible.

It is advisable when deemed appropriate that information on serious and unexpected adverse reactions (RAGI) be presented in a list together with a brief analysis of the data provided.

Researchers must also be informed of the safety aspects that impact the conduct of the clinical trial or the development of the product. Including disruption of the development program or security-related protocol modifications.

Follow-up of subjects after adverse events will be performed by clinical and complementary examinations necessary for the duration of treatment and then on a monthly basis during follow-up and up to 30 days after the end of treatment. In the event of a possible pregnancy, the health status of both the mother and the newborn will be monitored during the trial, whether the person who has become pregnant is the one who is taking the investigational drug or if it has been taken by her partner.

No interim analyses are planned for the present study.

11. Statistics

11.1 Sample

The study will be carried out in 60 patients. This is a proof of concept and does not require an ad-hoc sample size calculation.

11.2 Sample size

11.3 Analysis

Comparison of patient proportions will be performed using Fisher's exact test and the 95% confidence interval will be calculated for the difference in proportions.

Quantitative data at baseline and after 24 weeks, as well as absolute and relative changes at 24 weeks, will be compared using the Wilcoxon rank sum test. The point estimate and 95% confidence interval of the difference in medians will be estimated using the Hodges-Lehman methodology using the Moses free distribution.

Correlations between continuous variables will be evaluated using Spearman's rank correlation test.

The study of baseline predictors of response will be carried out by means of a multivariate analysis of multiple logistic regression.

Limitations of the study:

Although the hypothesis of the study has been based on various congruent information that allow us to face with sufficient guarantee the feasibility of the study and the eventual demonstration of the virological and immunological efficacy of the ATRIPLA® dose reduction strategy, we are not absolutely certain that an unacceptably high virological failure rate (standard viral load ≥ 37 copies/mL on two consecutive occasions) may occur in the experimental arm. We will consider a priori that the failure of at least 20% (n=6) of the patients in the experimental arm will represent an unacceptably high virological failure rate. In this case, its conclusion will be considered premature. In this extreme case, the data of the patients already included would be analyzed.

This study, even with the most favorable virologic and immunological results, would not constitute definitive proof of the safety and efficacy of ATRIPLA®'s dose reduction strategy. The present study is only a proof of concept and another study with a sufficiently large sample size would be needed to adequately demonstrate the non-inferiority of the strategy. The results of the present study can help to design the non-inferiority study and to estimate its sample size.

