Our study aims to conceptually confirm whether dose reduction of ATRIPLA® is feasible as a strategy and whether it entails any virological or immunological risk. If the results of this study are positive, they could form the basis for a randomized clinical trial of sufficient size to attempt to validate this strategy for future clinical use.

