6.1 Primary and Secondary Endpoints**Primary Endpoint:**

The primary endpoint of the study will be the proportion of patients who continue to have a standard plasma viral load (<37 copies/mL) at 24 weeks by intention-to-treat analysis.

Secondary endpoints:

- 1) The proportion of patients with ultrasensitive viral load (<1 copy/mL) after 24 weeks.
- 2) The change from baseline to 24 weeks in the viral reservoir of peripheral blood mononuclear cells
- 3) Changes from baseline to 24 weeks in TREC production, immune profile of activation (CD38 and HLA-DR) and senescence (CD57 and CD28) in CD4 and CD8 lineages, in naïve and effector and memory T cell ratios (CCR7 and CD45RA), and changes in apoptosis levels in vitro by annexin V staining.
- 4) Changes in plasma levels of efavirenz.
- 5) Changes in sleep quality (Pittsburgh Sleep Quality Index), plasma levels of vitamin D and lipids, and estimated glomerular filtration rate.
- 6) Overall safety (reporting side effects, serious side effects, and discontinuation of treatment due to side effects)

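### Section 11.3 tests each of at least nine immunological change endpoints in up to three overlapping ways and does not say which comparison counts

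*Combined protocol and SAP*

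**What the plan says.** The closing paragraph of the justification (section 4, just before 4.1) gives as an aim to learn whether dose reduction is feasible and "whether it entails any virological or immunological risk". The study title also names immunological safety.

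Section 6.1, secondary endpoint 3, carries the immunological part. It begins "Changes from baseline to 24 weeks in TREC production, immune profile of activation (CD38 and HLA-DR) and senescence (CD57 and CD28", specified for both T-cell lineages, and goes on to naïve, effector and memory T-cell proportions and annexin V apoptosis. The endpoint is worded as change throughout. Section 1.13.2 of the summary does the same.

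Section 11.3 has one sentence on testing quantitative variables. It says that the baseline and week-24 values, "as well as absolute and relative changes at 24 weeks, will be compared using the Wilcoxon rank sum test". For estimation it adds that "The point estimate and 95% confidence interval of the difference in medians" will come from the Hodges-Lehmann method. I read these as between-arm comparisons, because the rank-sum test is for independent groups.

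Section 11.1 says "The study will be carried out in 60 patients" and that a proof of concept needs no sample size calculation. No alpha, multiplicity rule, preferred measure, direction of harm or size of harmful change is given for any immunological marker.

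**The concern.** The endpoint definition and the analysis do not match. Section 6.1 asks about change. Section 11.3 tests the week-24 value, the absolute change and the relative change, and also the baseline value, where randomisation makes the null hypothesis true. With nine or more markers this produces many overlapping p-values, and the plan does not say which one answers the question for a given marker.

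Two things follow. A chance p<0.05 somewhere in the panel is quite likely even if the reduced schedule is harmless. And for a marker that really shifts, the answer can depend on which of the tests is quoted. Sections 4 and 11.3 say the results are to inform a later, larger trial, so an ambiguous immunological reading would be carried forward. For virological failure, by contrast, sections 6.2 and 11.3 fix a threshold in advance.

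**Working it through.** The plan contains no calculation for these markers to reproduce. The one check available is arm size.

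**Inputs from the documents**
- Arm size: sections 6.2 and 11.3 equate 20% of the experimental arm with n=6, so 6 / 0.20 = 30. With 60 in total (11.1) this implies 30 v 30.
- Markers (6.1 item 3): TREC 1, CD38 and HLA-DR 2, CD57 and CD28 2, naïve/effector/memory 3, annexin V 1. The total is 9, and about 15-17 if most are counted separately in CD4 and CD8 cells.
- Post-baseline tests per marker (11.3): week-24 value, absolute change, relative change = 3. So 9 × 3 = 27 tests, or 36 with baseline.

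**Assumptions (not in the documents)**: two-sided 5%, suggested by the 95% intervals; log-normal markers; baseline-to-week-24 correlation r; between-marker correlation ρ; no dropout.

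**False positives with no effect**

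For one comparison on each of nine independent markers, 1 − 0.95^9 = 37%. For 27 independent tests, 1 − 0.95^27 = 75%, but this is too high because the three tests on a marker share data. Simulation at 30 v 30 with r = 0.7 gives, for at least one p<0.05 over nine markers:

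| | ρ = 0 | 0.3 | 0.5 | 0.7 |
|---|---|---|---|---|
| Any of three tests, two-sided | 63% | 57% | 47% | 40% |
| Any of three, harmful direction only | 38% | 34% | 26% | about 20% |
| One change test per marker | 36% | 32% | 27% | 20% |

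Repeat runs differ by a few points; across them, one change test per marker gives about 20-38%. With markers correlated in families (0.6-0.8 within, 0.2-0.4 between), any of three gives 45-59%. With 17 markers it gives 81-84% at ρ = 0 and 47-49% at ρ = 0.7.

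**Sensitivity to a shift of 0.5 between-patient SD on one marker**

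In between-patient SD units, the SD of the change is √(2(1 − r)). Allowing for rank-sum efficiency of 0.955, SE = SD × √(2/30) / √0.955. The 95% half-width is 1.96 × SE, and power is Φ(0.5/SE − 1.96).

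| | SD | Half-width | Power (formula) | Power (simulated) |
|---|---|---|---|---|
| Week-24 value | 1 | 0.52 | 47% | 45% |
| Change, r = 0.5 | 1 | 0.52 | 47% | 46% |
| Change, r = 0.7 | 0.775 | 0.40 | 69% | 69% |
| Change, r = 0.8 | 0.632 | 0.33 | 85% | 84% |

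Simulated half-widths agree to within 0.01 SD. Reading any of the three tests as a detection gives 64% / 79% / 90% at r = 0.5 / 0.7 / 0.8. The week-24 and absolute-change tests disagree on significance in 31% / 38% / 44% of such trials, so the unstated choice often decides the result.

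**The case against.** The strongest reply is that these are secondary endpoints in a declared proof of concept. Section 11.3 attaches no decision to a p-value on any marker, plans point estimates and 95% intervals, and says that even the most favourable virologic and immunological results would not be definitive proof. Much of this stands. It rules out treating the gap as a flaw in a confirmatory claim, and it is why neither a larger sample nor a multiplicity correction is called for. It does not settle which comparison represents each marker, and the caution is directed at favourable results, not at an isolated adverse marker.

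Four stronger readings are tempting, and the documents do not support them:
- *At least half of harmless trials would flag a marker.* This is not a floor. The rate falls to about 40% at between-marker correlation 0.7, and it is lower when only harm counts. The documents give none of the correlations that fix it.
- *A 0.5-SD harm is often missed.* That holds for the week-24 value, but 6.1 defines the endpoint as change. On a stable marker (r = 0.8) the change test detects about 84%. It is also inconsistent to count any of three tests for false positives but only one for misses.
- *The study cannot exclude 0.5 SD.* For change, an observed difference of zero would exclude it at r = 0.7 or 0.8 (half-widths about 0.41 and 0.33), though not at 0.5.
- *One marker must be made the lead.* Nothing in the plan ranks activation above TREC or senescence, and a broad panel is a legitimate aim. That choice belongs to the investigators.

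**Conclusion.** The point holds as a mismatch between 6.1 and 11.3. The endpoint is change, yet the analysis adds week-24-only tests, two versions of change and baseline tests, with no deciding comparison and no rule for reading the panel. Under the assumptions above, about 40-60% of no-effect trials show some p<0.05, or about 20-40% in the harmful direction. One change comparison per marker brings the two-sided rate to about 20-38%. These are illustrations that depend on correlations the documents do not give. Counting lineages separately raises them. Missing samples, which 11.5 leaves unimputed, would reduce power: at 27 per arm and r = 0.7 the change test detects about 62%.

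This is a worthwhile, inexpensive improvement. It does not undermine the trial or its primary endpoint.

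**What to change.** In 6.1 item 3 and 11.3:
1. For each immunological marker, name one between-arm comparison: a single change measure (absolute or relative, chosen in advance) with its direction of harm.
2. Remove the week-24-only tests, the duplicate change tests and the baseline significance tests. Baseline values can be described without p-values.
3. Label the panel exploratory and report the Hodges-Lehmann estimate with its 95% interval for every marker. State that no significance claim will rest on an isolated marker, and that p≥0.05 will not be read as absence of immunological risk.
4. Optionally, name a lead marker, chosen by the investigators.

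The cost is a few sentences, with no new data, visits or patients. The downside is that isolated p<0.05 results can no longer be claimed. The change does not make the study larger: for a shift of 0.5 SD of the change itself, one rank-sum test at 30 per arm still has about 47% power, and 80% would need 63 per arm (normal approximation). That is why the intervals should carry the message.

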1.13.2. Secondary

- Percentage of patients with virologic response viral load <1 copy/mL after 24 weeks.
- Change from baseline to 24 weeks in the viral reservoir of peripheral blood mononuclear cells
- Changes from baseline to 24 weeks in REBT production
- Changes in the immune profile of activation (CD38 and HLA-DR) and senescence (CD57 and CD28) in the CD4 and CD8 lineages, and in the proportions of naïve and effector and memory T cells (CCR7 and CD45RA).

- Changes in apoptosis levels in vitro by annexin V staining.
- Changes in plasma levels of efavirenz.
- Changes in sleep quality (Pittsburgh Sleep Quality Index), plasma levels of vitamin 25OH-D and lipids, and estimated glomerular filtration rate (CPK-EPI).
- Overall safety (reporting side effects, serious side effects, and discontinuation of treatment due to side effects)

1.14. Study population and total number of patients:

Adult patients with well-controlled chronic HIV infection and on treatment with ATRIPLA.® A total of 60 patients will be included.

1.15. Duration of treatment:

The approximate expected duration for the inclusion of patients is 12 months, and the duration of treatment and follow-up of the included patients will be extended by a maximum of 24 weeks.

1.16. Schedule and expected completion date:

The study is expected to begin, once the permits have been obtained, in March 2013. The recruitment period will be 48 weeks. The follow-up of the patients will last 24 weeks to start the study. The study is expected to be completed in October 2014.

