- Immunological study including: production of TREC, immune profile of activation (CD38 and HLA-DR) and senescence (CD57 and CD28) in CD4 and CD8 lineages, apoptosis (annexin V staining), and ratios of naïve T cells and effectors and memory cells (CCR7 and CD45RA).
- Pharmacokinetic study, including baseline plasma levels of efavirenz at the beginning and end of the study.
- Safety study, including: sleep quality test (Pittsburgh Sleep Quality Index), vitamin 25OH-D levels, estimated glomerular filtration rate (CPK-EPI) and plasma lipids (triglycerides, total cholesterol and HDL) at the beginning and end of the study, as well as general tolerability.

6. Trial Design

Open-label study, Phase IV, pilot, prospective single-center.

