All laboratory specimens should be obtained prior to administration of the first dose of study medication.

(#) These visits will be made only to patients who are in the experimental treatment arm (3-day-per-week treatment)

& At baseline visit it is advised to perform a blood pregnancy test

* Genotypic resistance testing will be performed if the patient has virologic failure (defined by HIV-1 plasma viral load >50 copies/mL confirmed on two consecutive occasions)

Blood biochemistry: lipids (TG, total cholesterol and HDL), creatinine and estimated glomerular filtration rate (CPK-EPI), levels of 25OH vitamin D.

Hematology: Blood count

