6.5 Trial duration

The approximate expected duration for the inclusion of patients is 12 months, and the duration of treatment and follow-up of the included patients will be extended by a maximum of 24 weeks

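### Vitamin D change over 24 weeks is compared between arms with no allowance for entry date, which gives up precision that could be recovered cheaply

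*Combined protocol and SAP*

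**What the plan says.** Section 6.1 lists among the secondary endpoints "Changes in sleep quality (Pittsburgh Sleep Quality Index), plasma levels of vitamin D and lipids, and estimated glomerular filtration rate". Vitamin D belongs to the blood biochemistry panel; the footnote to the schedule in 6.2 names "creatinine and estimated glomerular filtration rate (CPK-EPI), levels of 25OH vitamin D". The schedule marks that panel at Day 0 and week 24 only, for both arms. Section 5 likewise places the safety measurements, vitamin D and "plasma lipids (triglycerides, total cholesterol and HDL) at the beginning and end of the study" among them, at those two points.

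On timing, section 6.5 states "The approximate expected duration for the inclusion of patients is 12 months" and that "the duration of treatment and follow-up of the included patients will be extended by a maximum of 24 weeks". Section 1.16 of the synopsis gives the accrual window as "The recruitment period will be 48 weeks" and adds "The study is expected to begin, once the permits have been obtained, in March 2013".

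On analysis, section 11.3 says that baseline values, week-24 values and "absolute and relative changes at 24 weeks, will be compared using the Wilcoxon rank sum test", with a Hodges-Lehmann estimate and 95% confidence interval for the difference in medians. The only multivariable model in 11.3 is a logistic regression for predictors of response. Season, sample date and stratification by date are not mentioned anywhere.

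**The concern.** 25OH vitamin D depends on sun exposure and so can be expected to follow a yearly cycle. With two samples nearly half a year apart, each patient's change contains almost the full seasonal contrast, and its sign and size depend on the month of entry. A patient entered in March is compared with late summer, and one entered in September with late winter. Entry spread over about a year puts the whole range of these contrasts into each arm.

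An unadjusted rank sum test treats that spread as random noise, although most of it could be predicted from the date of entry. At stake is the width of the interval for the arm difference in vitamin D, in a trial with about 30 patients per arm. A secondary question is whether the change from baseline inside one arm can be read by itself.

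**Working it through.** **Inputs from the documents.** Total 60 patients (11.1). The 20% = 6 rule for the experimental arm (6.2, 11.3) implies 6/0.20 = 30 per arm. Sampling interval 24 weeks. Entry over 48 weeks (1.16) or about 12 months (6.5). The plan gives no SD, effect size or power for vitamin D, so it has no figure to reproduce.

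**Assumptions not in the documents.** Season is a sinusoid with a 52-week period and amplitude A = 2.5, 5 or 7.5 ng/mL (peak to trough 5, 10 or 15), the same for all patients. The non-seasonal SD of the 24-week change is 6, 8 or 10 ng/mL.

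**Step 1: seasonal part of a 24-week change.** Its amplitude is 2A·sin(π·24/52) = 1.985A. With even year-round entry its variance is (1.985A)²/2 = 1.971A², an SD of 1.404A.

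**Step 2: variance inflation.** The ratio is 1 + 1.971(A/SD)².

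| SD | A = 2.5 | A = 5 | A = 7.5 |
|---|---|---|---|
| 6 | 1.34 | 2.37 | 4.08 |
| 8 | 1.19 | 1.77 | 2.73 |
| 10 | 1.12 | 1.49 | 2.11 |

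At SD 8 and A = 5 the total SD is √(64 + 1.971·25) = 10.64. The standard error of the difference in mean change, SD·√(2/30), rises from 2.07 to 2.75 ng/mL.

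**Step 3: effect on the planned test.** This was simulated with 4,000 runs per scenario, 30 per arm, even entry over 48 weeks from March and SD 8. The true difference was 5.79 ng/mL, which has 80% power without season by the normal approximation.

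| A | Rank sum on change | Linear model with sine and cosine of entry date |
|---|---|---|
| 0 | 77% | 77% |
| 2.5 | 69% | 77% |
| 5 | 52% | 77% |
| 7.5 | 36% | 77% |

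With no true difference, both methods rejected in 4 to 5% of runs, and the mean arm difference was 0.00 to 0.04 ng/mL. The full recovery of power is a best case, because the simulated season had exactly the form that was fitted.

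**Step 4: mean change within one arm.** With even entry over L weeks, the seasonal part of the arm mean is at most 1.985A·sin(πL/52)/(πL/52).

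| Entry window | Upper bound | At A = 5 |
|---|---|---|
| 52 weeks | 0 | 0 |
| 48 weeks | 0.16A | 0.8 ng/mL |
| 36 weeks | 0.75A | 3.8 ng/mL |
| 24 weeks | 1.36A | 6.8 ng/mL |

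These are worst cases over the choice of months. A simulated 24-week window starting in March, with the seasonal peak assumed in late August, gave a shift of only 0.8 ng/mL at A = 5. Rises early in that window and falls later in it nearly cancel.

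**The case against.** The strongest reply is that nothing here invalidates the planned analysis. The rank sum test is a two-sample test, most naturally read as arm against arm, and the daily-dose arm is randomised, concurrent and sampled at the same two visits. A seasonal drift shared by both arms drops out of the comparison. Chance imbalance in entry month has an SD of 1.985A/√2·√(2/30) = 0.36A, but it is already part of the test's error rate. All of this stands. Covariate adjustment is a gain in efficiency here and does not correct a bias.

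A reader might infer more, in three ways that the documents do not support.

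- **That within-arm change is uninterpretable.** The year-round entry that creates the noise also makes the seasonal shift nearly cancel in the arm average. A spurious shift of about 10 ng/mL at A = 5 (1.985 × 5 = 9.9) would need every patient to enter on the same date. The plan names no paired or within-arm test. Two things remain. Section 11.3 does not say which groups its comparison sentence refers to. Also, 6.2 and 11.3 allow an early end after six failures in the experimental arm, with analysis of those already included, which could shorten the entry window.
- **That the noise is certainly large.** The inflation runs from 1.12 to 4.08 over the assumed values, and neither input is in the documents.
- **That season exceeds the drug effect.** The documents give no expected effect on vitamin D to compare it with.

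The stakes are also low. Vitamin D is one item in the fifth of six secondary endpoint groups, no decision rule depends on it, and 11.1 makes no sample size calculation.

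**Conclusion.** The point holds as a matter of precision. Section 11.3 leaves out a predictor of vitamin D change that is known at entry, in a design whose sampling interval comes close to maximising the seasonal contrast. The between-arm comparison is unbiased and keeps its type I error. Its variance is inflated about 1.1 to 4.1 times for amplitudes of 2.5 to 7.5 ng/mL and non-seasonal SDs of 6 to 10 ng/mL, and 1.77 times at the middle values. The true inflation is unknown, because both inputs are assumptions.

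Within-arm change is a conditional concern: the bound is 0.16 of the amplitude with even 48-week entry, and up to 1.36 of it if entry is confined to an unfavourable 24-week window. Severity is low.

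**What to change.** In 11.3, prespecify for vitamin D one of the following between-arm comparisons:

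- a linear or rank-based model for the week-24 value with arm, baseline value, and sine and cosine of the day of year of the baseline sample; or
- a van Elteren rank sum test stratified by calendar quarter of entry. This stays closer to the planned method but removes only the seasonal variation between quarters.

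Add that the comparison is between arms, that entry month will be reported by arm, and that within-arm vitamin D change is not read as a treatment effect without the control arm.

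The cost is two to three degrees of freedom and slightly more analysis work. No extra visit, sample or patient is needed, since the baseline date is known for everyone enrolled. With 60 patients, four quarters would average 15 each, so uneven entry could leave thin strata; the sine and cosine version avoids this. Fixing the choice now also avoids having to justify it later as a deviation under 11.6.

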The specific PCR product obtained with the primers specific for a conserved region of the gag gene previously described by Palmer et al (20) will be cloned into a pGEM-T Easy Vector (PROMEGA) plasmid that will be linearized by the restriction enzyme Spel (NEW ENGLAND BIOLABS). This plasmid, which contains a T7 promoter for RNA polymerase, will be transcribed in vitro using the commercial MEGAscript Kit (AMBION). Purification of the RNA transcript obtained as a standard control for HIV-1 quantification will be performed using the commercial MEGAclear Kit (AMBION). The concentration and integrity of the RNA transcript obtained will be determined using the BioAnalyzer (AGILENT) platform. From a known concentration of this standard standard, a bank of dilutions will be generated to determine the efficiency, linearity range and lower limit of sensitivity.

The RNA transcript used as an internal control, based on a conserved region of the coding sequence of the M1 protein of the influenza A virus, has previously been used in the quantification of the influenza A (H1N1) pdm09 virus in our laboratory (Almansa et al [PMID 21880131], Anton et al [PMID 20955912]). For its synthesis, the methodology described in the previous section was followed. The percentage of internal control, added to the plasma sample prior to ultracentrifugation, which is recovered and from which we will consider the results of the HIV-1 viral load valid, will be validated in our laboratory, initially considering as good the 55% recovery previously described by Palmer et al (20).

B) HIV-1 viral reservoir study:

The study of the viral reservoir will be determined based on the methodology initially described by the group of Nicholas Chomont (19) modified by the Laboratory of [name]. It will be made from 50×10^6 frozen peripheral blood mononuclear cells. A purification of CD4+ T-cells by negative depletion will be performed. These purified cells will be activated in the presence of anti-CD3/CD28. The culture should be maintained for 9 days in the presence of a cocktail of antiretrovirals (zidovudine, efavirenz, and raltegravir) to prevent further rounds of infection and a reactivation of viral production. Finally, viral production will be quantified at 3, 6 and 9 days, from the supernatant of the cultures, by ultrasensitive RT-qPCR and p24 antigen assessment by capture ELISA.

C) Immunological studies:

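### Section 11.3 presents the Hodges-Lehmann/Moses interval as that of the difference in medians, which fails for efavirenz, and it has no rule for undetectable reservoir values

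*Combined protocol and SAP*

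**What the plan says.** Section 11.3 applies one approach to every quantitative endpoint. Values at baseline and week 24, "as well as absolute and relative changes at 24 weeks, will be compared using the Wilcoxon rank sum test". The summary measure follows: "The point estimate and 95% confidence interval of the difference in medians will be estimated using the Hodges-Lehman methodology", with Moses distribution-free limits. The section states no shift assumption, no transformation, and no rule for tied or undetectable values.

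Two secondary endpoints in section 6.1 matter most here. One is "Changes in plasma levels of efavirenz". The other is the change in the peripheral-blood reservoir from baseline to week 24. Section 9.1 B describes the reservoir assay: CD4 cells are stimulated in culture and "viral production will be quantified at 3, 6 and 9 days", by RT-qPCR and p24 ELISA. The documents give no expected distribution, effect size or undetectable share for any of these markers.

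The ultrasensitive viral load is handled differently. It is listed as "The proportion of patients with ultrasensitive viral load (<1 copy/mL) after 24 weeks", so it falls under Fisher's exact test and the interval for a difference in proportions.

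**The concern.** The named quantity and the computed quantity are not the same. A pure shift moves a distribution without changing its spread. A multiplicative effect on a positive marker changes level and spread together, so the arms differ in shape. The median of pairwise differences then departs from the difference in medians, and a nominal 95% interval for the first need not cover the second 95% of the time.

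A second difficulty has a different cause. If many readouts are tied at the detection limit, most pairwise differences are exactly zero, and the estimate and both limits can be zero. The background text relies on the reservoir to show virological effects that standard viral load would miss. A line reading 0 (95% CI 0 to 0) could therefore be taken as evidence of no effect when it only reflects ties. The results are also meant to inform the later non-inferiority study.

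**Working it through.** **Per-arm size.** Section 11.1: "The study will be carried out in 60 patients". Section 11.3 sets its failure threshold at "the failure of at least 20% (n=6) of the patients in the experimental arm", so 6 / 0.20 = 30 in the experimental arm, and 60 − 30 = 30 in control.

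**The stated 95%.** With 30 × 30 = 900 differences, the Moses rank is approximately 450 − 1.96 × √(900 × 61 / 12) = 450 − 132.6 = 317.4, rounded up to 318. The interval runs from the 318th smallest to the 318th largest difference. From the exact Mann-Whitney distribution, its confidence under a pure shift without ties is 95.04%. The stated level is reproduced under that condition.

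**Skew alone.** For skewed markers with no effect or a pure shift, simulated coverage is 94.9 to 95.4%.

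**Efavirenz ratio implied by the documents.** The background text before section 4.1 gives a plasma half-life h of 40 to 55 hours. Section 8.1 gives daily versus Monday/Wednesday/Friday dosing, and section 9.1 D samples the experimental arm on Monday morning. Assume first-order elimination at steady state and write f(t) = 2^(−t/h).

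- Daily trough: f(24) / (1 − f(24))
- Monday trough: [f(72) + f(120) + f(168)] / (1 − f(168))
- h = 40: 0.493 / 1.939 = 0.254
- h = 55: 0.846 / 2.831 = 0.299

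The hour of dosing cancels if it is the same in both arms, because it multiplies both levels by the same factor.

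**Coverage at that ratio.** Lognormal week-24 values, 30 per arm, 10,000 simulated trials per cell. The log-SD is an assumption.

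| Ratio | log-SD 0.5 | log-SD 0.7 | log-SD 1.0 |
|---|---|---|---|
| 0.25 | 91.9% | 91.3% | 90.6% |
| 0.30 | 92.3% | 91.5% | 91.1% |

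Allowing for simulation error and slightly different runs, this is about 90.5 to 93%. The week-24 estimate is about 3 to 12% too small. On logs a constant ratio is a pure shift, and simulated coverage was 94.9 to 95.4%.

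**Change scores.** With group ratios of 1.5 to 3, log-SD 0.5 to 1.5 and baseline correlation 0.5 or 0.8, coverage was 90.9 to 94.5% for absolute changes and 88.4 to 94.6% for relative changes. The 3 to 12% figure belongs to week-24 values and should not be carried over to change scores.

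**Small effects.** At ratios of 0.8 to 1.2, coverage is 94 to 96%.

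**Collapse to 0 to 0.** Suppose k of 30 are undetectable in each arm, so k² differences are zero. Both limits are zero when fewer than 318 differences lie on each side of zero.

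- k = 18 (60%): 900 − 324 = 576, or 288 per side if evenly split. The interval collapses.
- k = 16 (53%): 900 − 256 = 644, so at least 322 lie on one side. It does not collapse.

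A change score is exactly zero only if the patient is undetectable at both visits. With 70% undetectable at each visit and no within-patient correlation, that is 0.7 × 0.7 = 49% of patients. The simulated share of trials with a 0 to 0 interval, under assumed undetectable shares equal in both arms, is:

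| Undetectable | Week-24 values | Change from baseline (correlation 0 to 0.8) |
|---|---|---|
| 60% | 38% | about 0 to 6% |
| 70% | 80% | about 5 to 43% |
| 80% | 98% | about 55 to 89% |

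With 80% undetectable in control and 60% in the experimental arm, the detectable share doubles from 20% to 40%, yet week-24 values still give 0 to 0 in about 46 to 47% of trials. In all these cases the true difference in medians is 0, so the interval covers it.

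**The case against.** Several stronger readings are tempting, and the documents do not support them.

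- *The interval fails for skewed markers in general, at about 91%.* It does not. Skew without a difference in shape costs nothing. Nothing in the documents suggests that TREC or triglycerides will halve or double in 24 weeks, and with small effects coverage stays near 95%. A figure near 91% fits efavirenz under assumed log-SDs; it is not a property of the plan.
- *The reservoir interval will read 0 to 0 whenever most values are undetectable.* The endpoint in section 6.1 is a change, for which collapse is much rarer than for single week-24 values at 60 to 70% undetectable. It becomes common only near 80%, and the share is unknown.
- *Collapse is a coverage failure.* It is not. The interval is uninformative about the detectable tail, but it contains the true difference in medians.
- *The trial would report proof of safety.* Section 11.3 itself says that even the most favourable results would not settle safety or efficacy.

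It is also fair to say that the efavirenz error is practically small. The discrepancy at week 24 is a few per cent of a 70 to 75% fall, and the interval excluded zero in 99 to 100% of simulated trials. The text is visibly translated, so the label may be looser than the protocol's source-language text; the documents cannot settle that.

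What survives is that the label is wrong without a shift, that one named endpoint breaks the shift condition on the documents' own figures, and that no rule exists for ties.

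**Conclusion.** The point holds as a minor correction to secondary analyses. For efavirenz at week 24, the interval as labelled covers about 90.5 to 93% instead of 95%. This rests on first-order kinetics, lognormal values, 30 evaluable patients per arm and a log-SD of 0.5 to 1.0; only the half-life, schedule and sampling day come from the documents. The collapse risk for the reservoir depends on an undetectable share and a within-patient correlation that the documents do not give, so it is a contingency to plan for and not a predicted result. The primary endpoint and the ultrasensitive viral load are proportions with their own method and are unaffected.

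**What to change.** In section 11.3:

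1. For efavirenz and other strictly positive, skewed markers, compute Hodges-Lehmann/Moses on the log scale and report a between-arm ratio with its 95% CI. For change from baseline, use log week-24 value minus log baseline value.
2. For the remaining quantitative markers, call the result the Hodges-Lehmann location shift (median of between-arm pairwise differences), not the difference in medians.
3. If about half or more of the reservoir values are undetectable, also report the difference in the proportion detectable with its 95% CI, beside the rank-sum result. Items 1 and 2 do not cure the collapse, so this rule is needed separately.

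The cost is a few sentences and slightly more output, with some results expressed as ratios. No new data, visits or patients are needed.
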